8.2.10 REPORTING REQUIREMENTS

This study is investigational new drug (IND) exempt. The following criteria must be met in order for a clinical investigation to be considered IND-exempt:

- (i) The investigation is not intended to be reported to FDA as a well-controlled study in support of a new indication for use nor intended to be used to support any other significant change in the labeling for the drug;
- (ii) If the drug that is undergoing investigation is lawfully marketed as a prescription drug product, the investigation is not intended to support a significant change in the advertising for the product;
- (iii) The investigation does not involve a route of administration or dosage level or use in a patient population or other factor that significantly increases the risks (or decreases the acceptability of the risks) associated with the use of the drug product;
- (iv) The investigation is conducted in compliance with the requirements for institutional review set forth in part 56 and with the requirements for informed consent set forth in part 50; and
- (v) The investigation is conducted in compliance with the requirements of § 312.7.

StrataPATH meets the above criteria. This trial will be conducted in compliance with the requirements for review by an IRB (21 CFR part 56) and with the requirements for informed consent (21 CFR part 50).

8.3 UNANTICIPATED PROBLEMS

8.3.1 DEFINITION OF UNANTICIPATED PROBLEMS (UP)

The information contained in this protocol and all other information relevant to this study are confidential and proprietary information of Strata Oncology Inc., except as may be required by federal, state or local laws or regulation, and may not be disclosed to others without prior written permission of Strata.

Page 44 of 56

The Office for Human Research Protections (OHRP) considers unanticipated problems (UPs) involving risks to participants or others to include, in general, any incident, experience, or outcome that meets **all** the following criteria:

- **Unexpected** in terms of nature, severity, or frequency given (a) the research procedures that are described in the protocol-related documents, such as the IRB approved research protocol and informed consent document; and (b) the characteristics of the participant population being studied, **and**
- **Related or possibly related** to participation in the research (“possibly related” means there is a reasonable possibility that the incident, experience, or outcome may have been caused by the procedures involved in the research), **and**
- Suggests that the research places participants or others at a **greater risk of harm** (including physical, psychological, economic, or social harm) than was previously known or recognized.

8.3.2 UNANTICIPATED PROBLEM REPORTING

The investigator will report unanticipated problems to the reviewing IRB and to the study sponsor. The UP report will include the following information:

- Protocol identifying information: protocol title and number, PI's name, and the IRB project number.
- A detailed description of the event, incident, experience, or outcome.
- An explanation of the basis for determining that the event, incident, experience, or outcome represents an UP.
- A description of any changes to the protocol or other corrective actions that have been taken or are proposed in response to the UP.

To satisfy the requirement for prompt reporting, UPs will be reported using the following timeline:

- UPs that are adverse drug reactions (ADRs) will be reported to the study sponsor within 24 hours of the investigator becoming aware of the event. The event must be ultimately reported to the IRB within 1 week from the time of identification of the event.
- Any other UP will be reported to the study sponsor within 5 business days of the investigator becoming aware of the problem. The event must be ultimately reported to the IRB within 2 weeks from the time of identification of the event.

9 STATISTICAL CONSIDERATIONS

9.1 SAMPLE SIZE DETERMINATION

The information contained in this protocol and all other information relevant to this study are confidential and proprietary information of Strata Oncology Inc., except as may be required by federal, state or local laws or regulation, and may not be disclosed to others without prior written permission of Strata.

Page 45 of 56

The study design is similar to a basket trial with each basket molecularly defined. For both cohorts (tdMeta and μ Meta), sample size calculations were completed under the following assumptions:

- Each cohort will enroll unique participants. Although participants may qualify for enrollment in more than one cohort, they will be enrolled in only one biomarker cohort (Refer to Section 10.2 for definitions).
- Each molecularly defined cohort will be evaluated independently.
- tdMeta and μ Meta cohorts will be evaluated independently.

Sample size was determined using a two-stage design based on minimizing the risk of a false negative result. The binomial probability of observing an exact number of responses was used similar to that in a Simon's two-stage design.^{19,20} The null hypothesis that the true response rate is 0.05 will be tested against a one-sided alternative. In the first stage, 12 patients will be accrued per cohort. If there are 1 or fewer responses in these 12 patients, the study will be stopped for that cohort. Response will be defined as partial response or complete response for tdMeta cohorts and <50% ctDNA mean VAF ratio for μ Meta cohorts. Otherwise, 23 additional patients will be accrued for a total of 35. The null hypothesis will be rejected if 6 or more responses are observed in 35 patients. This design yields a type I error rate of 0.001 and a power of 88% when the true response rate is 0.30.

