9.3.6 PLANNED INTERIM ANALYSES

For each cohort, 12 participants will be enrolled initially. If there is one response or no responses in these 12 participants as defined by CR or PR (for tdMeta) and ctDNA response (for μ Meta), the study will be stopped in that cohort. A minimum rwRR/ctDNA response of 10% and risk-benefit profile that the sponsor deems promising will be required before an additional 23 participants will be accrued for a total of 35 participants.

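### Section 9.1 says the two-stage design minimizes the false-negative risk, but the written 12/35 rule does not: it misses 9.9% of cohorts at a true 30% response rate, mostly through the stage-1 stop

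*Protocol*

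**What the plan says.** Section 9.1 gives the design criterion: "Sample size was determined using a two-stage design based on minimizing the risk of a false negative result". It then fixes the rule:

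- Null: "The null hypothesis that the true response rate is 0.05 will be tested against a one-sided alternative".
- Stage 1: "In the first stage, 12 patients will be accrued per cohort", and "If there are 1 or fewer responses in these 12 patients, the study will be stopped for that cohort".
- Stage 2: "Otherwise, 23 additional patients will be accrued for a total of 35".
- Final decision: "The null hypothesis will be rejected if 6 or more responses are observed in 35 patients".

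The paragraph ends with a type I error of 0.001 and a power of 88% at a true rate of 0.30. It names no target for either error.

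Section 9.3.6 repeats the stage-1 stop ("If there is one response or no responses in these 12 participants as defined by CR or PR", with ctDNA response taking that role in the μMeta cohorts). It adds two conditions for going on: a minimum response of 10%, and a "risk-benefit profile that the sponsor deems promising will be required before an additional 23 participants will be accrued".

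**The concern.** A design that minimizes false negatives should leave no clearly better way to protect active cohorts at the same size. Yet the figures printed in the same paragraph imply a 12% miss risk beside a 0.1% false-positive risk, and stopping on a single response in 12 is a demanding early hurdle for a cohort with a true rate of 20% to 30%.

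The study is signal-finding, with up to 20 cohorts of 35. A stage-1 closure ends the study for that drug and biomarker pair. A reader told that false negatives were minimized may trust such a closure more than the rule warrants, and the protocol gives no miss risk for any true rate other than 30%.

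**Working it through.** **Inputs** (section 9.1): n1 = 12; stop if X1 ≤ 1; N = 35, so 23 more in stage 2; reject if the total is 6 or more; null rate 0.05; alternative 0.30. The rates 0.20 and 0.25 are added here to show how the miss risk changes. The sponsor's risk-benefit judgement in 9.3.6 is not modelled; it can only add misses.

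**Formulas.** With stop boundary r1 and final cut-off c:

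- P(stage-1 stop) = P(Bin(12, p) ≤ r1)
- P(reject) = Σ over x from r1 + 1 to 12 of P(Bin(12, p) = x) × P(Bin(23, p) ≥ c − x)
- Miss risk = 1 − P(reject) at an active rate

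**1. The plan's own figures.** With r1 = 1:

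| Final cut-off | Type I error (5%) | Power (30%) |
|---|---|---|
| 6 or more (as written) | 0.0052 | 90.1% |
| 7 or more | 0.0012 | 87.5% |
| Stated in 9.1 | 0.001 | 88% |

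The stated pair does not belong to the written cut-off. To the precision given, it fits 7 or more.

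**2. Miss risk of the written rule** (r1 = 1, c = 6):

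| True rate | Stage-1 stop | Missed at final look | Total miss risk |
|---|---|---|---|
| 30% | 8.5% | 1.4% | 9.9% |
| 25% | 15.8% | 4.7% | 20.5% |
| 20% | 27.5% | 12.1% | 39.6% |

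At 30% the stage-1 term is 0.7^12 + 12 × 0.3 × 0.7^11 = 0.0138 + 0.0712 = 0.0850. Its share of the misses is 0.0850 / 0.0986 = 86%. While this stop stands, no final cut-off can bring the miss risk at 30% below 8.5%.

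**3. Is the miss risk at a minimum?** The same 12 and 35, with other boundaries, for comparison only:

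| Stop / reject | Type I error | Miss at 30% | Stage-1 stop at 5% | Expected N at 5% |
|---|---|---|---|---|
| ≤1 / ≥6 (written) | 0.0052 | 9.9% | 88% | 14.7 |
| 0 / ≥7 | 0.0015 | 7.3% | 54% | 22.6 |
| 0 / ≥6 | 0.0068 | 3.7% | 54% | 22.6 |

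Expected N = 12 + 23 × (1 − P(stage-1 stop)): 12 + 23 × 0.118 = 14.7 and 12 + 23 × 0.460 = 22.6.

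The second row is lower on both errors at the design's own null and alternative. The gain in miss risk is specific to the 30% alternative: by the same formula that rule misses 20.3% at a true 25% and 44.4% at 20%, against 20.5% and 39.6% for the written rule. The third row misses less than the written rule at 20% as well (29.3%), for a small rise in type I error. Either row shows that the written rule does not minimize the false-negative risk.

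**4. If 7 or more was intended.** With r1 = 1 and c = 7 the miss risk is 12.5% at 30% and 50.7% at 20%, so the claim fits less well. In that case stopping only at 0 of 12 with the same cut-off lowers the miss at 30% from 12.5% to 7.3%, while type I error goes from 0.0012 to 0.0015. It is then no longer better on both errors, but the miss risk is still not at its minimum.

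**The case against.** The best defence is that the disputed words drive nothing. They set no boundary, sample size or analysis. The same paragraph prints the stop rule and a power of 88%, so it discloses a 12% miss risk, more than the 9.9% that the written rule carries at 30%. Power of about 90% is conventional. All of this stands, and it makes the point a wording correction and not a design failure. It does not make the sentence true.

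Four stronger readings are tempting, and the documents do not support them:

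- **The rule does the opposite of its stated aim.** A reader might infer this from the ratio of the two errors: 0.12 / 0.001 = 120 on the stated figures, about 19 on the exact ones (0.0986 / 0.0052). The ratio shows much stronger protection against false positives than against false negatives. It does not show that false negatives were ignored.
- **Most active cohorts close at stage 1.** Stage 1 closes 8.5% of cohorts with a true 30% rate. The 86% is a share of the missed cohorts.
- **The rule was chosen as optimal for alpha 0.01 and power 0.90.** A search over two-stage designs with N up to 45 does return 12/35 with these boundaries as the smallest expected N under the null for that pair. The protocol states no such targets, and the match depends on them: with alpha 0.01 and power 0.88 the minimum becomes stop at 0 of 7 and reject at 5 or more of 28 (expected N 13.3). Intent cannot be read back from this.
- **The stage-1 stop should become 0 of 12.** That is a trade-off, since expected enrolment in an inactive cohort rises from 14.7 to 22.6. It would also collide with section 9.3.6, where the 10% minimum blocks one response in 12 (8.3%). The gain in power would not be realised as the text stands.

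**Conclusion.** The concern holds as a misstatement of the design's property. Section 9.1 claims that the false-negative risk is minimized. The written rule has a miss risk of 9.9% at a true 30%, 20.5% at 25% and 39.6% at 20%, with 86% of the misses at 30% occurring at stage 1. Other boundaries at the same 12 and 35 miss fewer active cohorts at 30%, one of them with a lower type I error too. What the written rule gains is early closure of inactive cohorts.

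The figures assume that the cut-off of 6 or more is the intended one, that the binomial model holds with a single true rate per cohort, and that the sponsor's judgement in 9.3.6 stops no further cohorts. If 7 or more is intended, the miss risk is higher at every rate considered. That readers will over-trust a stage-1 closure is a plausible consequence, not something the protocol shows.

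**What to change.** In section 9.1, end the sentence quoted at the start after the words that name the two-stage design, and drop the clause about false negatives. In its place, state the exact operating characteristics of the rule: type I error at 5%, power at 30%, the share of the miss risk that falls at stage 1, and the miss risk at 20% and 25%.

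Make this edit together with reconciling the cut-off and the stated error rates. If 6 or more stands, report 0.0052 and 90.1%, with misses of 9.9%, 20.5% and 39.6% at 30%, 25% and 20%. If 7 or more is intended, correct the cut-off and report 0.0012 and 87.5%, with misses of 12.5% at 30% and 50.7% at 20%, and compute 25% by the same formula.

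Do not add a statement that the rule is optimal for particular error targets unless the sponsor can document that they were used. Leave the stage-1 boundary as it is.

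The cost of the wording change is a protocol edit and a less favourable stated property. It alters neither enrolment nor conduct.

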The information contained in this protocol and all other information relevant to this study are confidential and proprietary information of Strata Oncology Inc., except as may be required by federal, state or local laws or regulation, and may not be disclosed to others without prior written permission of Strata.

Page 17 of 56

patients were treated with osimertinib as adjuvant therapy. The data demonstrates the potential benefit of moving targeted therapies to earlier disease states.

Importantly, 44% of patients treated with placebo in ADAURA had not recurred after 24 months. In the paradigm of treating all early-stage patients with EGFR-mutant NSCLC with osimertinib, a substantial proportion may be cured prior to osimertinib treatment, and hence, cannot derive benefit while being exposed to osimertinib for 2 years. This indicates an opportunity to leverage newer technologies – specifically, liquid biopsies – to explore and refine who should be treated with targeted therapies based on if circulating tumor cells are present in the blood post-surgery.

With advancements in both tissue and blood-based molecular technologies, including genomic and transcriptomic profiling, there is an opportunity to expand the clinical benefit of approved therapies to earlier in the disease process where there is improved opportunity for durable disease-free survival.

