This study may also include separate cohorts of patients in the micro-metastatic setting (as defined by ctDNA positive liquid biopsy) post-standard of care adjuvant therapy, but not yet having been identified as traditionally advanced or metastatic using standard of care imaging or biochemical testing. All therapies are FDA-approved in oncology with demonstrated safety profiles in the traditionally advanced setting; the toxicity profile may be different in the micro-metastatic setting. The utility of targeted therapy in the early-stage setting has been demonstrated with the approval of osimertinib for patients with EGFR-mutated NSCLC. The ADAURA trial demonstrated that osimertinib was well tolerated post-resection in patients with stage IB-III NSCLC; dose reductions due to adverse events occurred in 9% of patients in the treatment group.⁶ This was comparable to the 10% dose reduction rate observed in first-line patients with advanced NSCLC at the same recommended dose.⁷ Comparatively, the toxicity profile of immunotherapies in early-stage disease may not be as favorable. Dose discontinuation due to adverse events occurred in only 9% of patients with advanced melanoma treated with pembrolizumab in KEYNOTE-001, while 14% of melanoma patients that received pembrolizumab as adjuvant therapy post resection in KEYNOTE-054 experienced adverse event related dose discontinuation.^{8,9} Recently announced data from KEYNOTE-564, however, suggests that the toxicity profile of pembrolizumab when used as adjuvant therapy in patients with renal cell carcinoma following nephrectomy was consistent with previously reported studies with the anti-PD-1 therapy.¹⁰ To monitor risk and capture any differences in toxicity profiles between patient populations, full safety data collection will be collected in this study.

More information on the clinical data associated with each therapeutic study arm and known and expected benefits, risks, and reasonably expected adverse events (Aes) may be found in the corresponding appendices.

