Explore the relationship between serial ctDNA measurement and participant response to therapy.	N/A

Table B: StrataPATH Objectives and Endpoints for μ Meta Cohorts

μ Meta Cohorts

The information contained in this protocol and all other information relevant to this study are confidential and proprietary information of Strata Oncology Inc., except as may be required by federal, state or local laws or regulation, and may not be disclosed to others without prior written permission of Strata.

Page 20 of 56

OBJECTIVES	ENDPOINTS
Primary	
Evaluate ctDNA response rate at 6 months for participants who received an anticancer biomarker-guided therapy.	ctDNA response – Proportion of participants with a <50% ratio of mean VAF will be defined as ctDNA responders. Molecular response is calculated as a ratio of mean VAF on-treatment at 6 months compared to their baseline VAF.
Secondary	
Evaluate the ctDNA response rate at additional timepoints for participants who receive an anticancer biomarker therapy.	ctDNA response – Proportion of participants with a <50% ratio of mean VAF will be defined as ctDNA responders. Molecular response is calculated as a ratio of mean VAF on-treatment at additional timepoints compared to their baseline VAF.
Evaluate Disease-Free Survival (DFS) stratified by ctDNA status or response at different timepoints.	DFS – Time from initiation of treatment until disease recurrence or death from any cause.
Assess the correlation between ctDNA and Disease-Free Survival (DFS).	DFS – Time from initiation of treatment until disease recurrence or death from any cause.
Evaluate overall survival (OS) for participants who received an anticancer biomarker-guided therapy.	OS – Time from initiation of treatment until death from any cause.
Monitor and characterize the overall safety for participants in the biomarker cohorts	Incidence of serious adverse events (SAEs).

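### Section 9.1 applies one 5% null and one stated type I error (0.001) to the μMeta ctDNA endpoint without support, and the written rule does not give 0.001 even at a 5% null

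*Protocol*

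**What the plan says.** Section 9.1 opens its sample size assumptions for tdMeta and μMeta together and gives a single hypothesis: "The null hypothesis that the true response rate is 0.05 will be tested against a one-sided alternative". The rule is also single. Stage 1 has 12 patients in each cohort, and its stopping rule reads: "If there are 1 or fewer responses in these 12 patients, the study will be stopped for that cohort". A cohort that continues adds 23 patients, which makes 35. The null is rejected at 6 or more responses in 35, and the section states a type I error of 0.001 and 88% power at a true rate of 0.30.

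The endpoint is what differs: "Response will be defined as partial response or complete response for tdMeta cohorts and <50% ctDNA mean VAF ratio for μ Meta cohorts". For the μMeta primary endpoint, Table B in section 3.1 adds the timing: "Molecular response is calculated as a ratio of mean VAF on-treatment at 6 months compared to their baseline VAF".

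Section 2.3 describes the μMeta population as micro-metastatic, "as defined by ctDNA positive liquid biopsy) post-standard of care adjuvant therapy, but not yet having been identified as traditionally advanced or metastatic". Section 2.2 says the two settings are to be kept apart in design and analysis, with different endpoints. Section 3.2.2 supports ctDNA response as an early predictor of therapy response and gives no background rate for it. Section 9.3.6 repeats the stage 1 stop for both cohort types and adds a shared 10% minimum response and a sponsor judgement on risk and benefit.

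**The concern.** A null rate for a single-arm response test should be the rate expected without an effective drug. A RECIST response and a follow-up VAF below half of baseline are different events, and no passage shows that both occur at 5% without one. For μMeta, the 5% is carried over and not justified.

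The protocol gives grounds for asking. μMeta patients enter after adjuvant therapy, and section 5.2 bars systemic anticancer therapy only within 3 weeks of the first dose, so some baseline values might still be falling. No minimum baseline VAF is set for the ratio. These are reasons to justify the figure. They do not show that it is too low.

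ctDNA response is the only μMeta primary endpoint, and there is no control arm. If the no-drug rate is above 5%, a cohort could be declared active, and considered for expansion, more often than section 9.1 tells the reader. A second defect sits in the same sentence: the stated error rates do not belong to the stated cut-off, in either cohort type.

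**Working it through.** **Inputs, all from section 9.1.** Stage 1 n = 12, stop at 1 or fewer; stage 2 n = 23, total 35; reject at r = 6 or more; null 0.05; alternative 0.30; stated type I error 0.001 and power 88%.

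**Formula.** The probability of passing at true rate p is

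P(pass) = Σ (x = 2 to 12) P[Bin(12, p) = x] × P[Bin(23, p) ≥ r − x].

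**Step 1: reproduce the stated figures (p = 0.05, r = 6).**

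| x in stage 1 | P(x of 12) | P(stage 2 ≥ 6 − x) | Product |
|---|---|---|---|
| 2 | 0.09879 | 0.02581 | 0.00255 |
| 3 | 0.01733 | 0.10517 | 0.00182 |
| 4 | 0.00205 | 0.32058 | 0.00066 |
| 5 | 0.00017 | 0.69264 | 0.00012 |
| 6 or more | 0.00001 | 1 | 0.00001 |

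The sum is 0.0052, about five times the stated 0.001. The same formula at p = 0.30 gives power 0.901, not 0.88. The stated pair does not reproduce.

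**Step 2: find the cut-off that does reproduce it.** With r = 7, P(pass) is 0.0012 at 0.05 and 0.875 at 0.30. These round to 0.001 and 88%. A single-stage test at 6 or more of 35 gives 0.0073 and 0.973, so ignoring the interim does not explain the figures. The mismatch is independent of the endpoint and affects tdMeta and μMeta alike.

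**Step 3: vary the μMeta no-drug rate.** The protocol gives no such rate, so the range is an assumption.

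| True no-drug rate | Pass at ≥6 of 35 (as written) | Pass at ≥7 of 35 | Pass at ≥8 of 35 |
|---|---|---|---|
| 5% | 0.0052 | 0.0012 | 0.0002 |
| 7% | 0.024 | 0.008 | 0.002 |
| 10% | 0.098 | 0.045 | 0.0175 |
| 15% | 0.337 | 0.223 | 0.128 |
| Power at 30% | 0.901 | 0.875 | 0.822 |

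Solving P(pass) = 0.05 for the written rule gives p of about 8.4%. Solving P(pass) = 0.001 gives about 3.6%, so the stated figure is true of the written rule only if the no-drug rate is about 3.6% or lower.

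**Step 4: does section 9.3.6 add protection?** Continuing past stage 1 already needs 2 of 12, or 16.7%. The 10% minimum response is therefore always met when the stop rule is passed, and does not change the table.

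**The case against.** A type I error is a property at the stated null, and a sponsor may choose 5%. No passage gives an untreated rate of VAF halving, and none shows that it exceeds 5%. If untreated micro-metastatic ctDNA clearly rises over 6 months, halving without an effective drug may be rare and 5% may be adequate. That stands, and it limits the point to a missing basis and a wrong figure.

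A reader might infer that an inactive drug will pass a μMeta cohort far more often than stated. The documents do not support that as a finding; it holds only if the no-drug rate is materially above 5%.

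A reader might also use section 2.1, "Importantly, 44% of patients treated with placebo in ADAURA had not recurred after 24 months", as a cured fraction and derive a share of false-positive entrants whose ctDNA reverts. The sentence reports non-recurrence at 24 months in one resected EGFR-mutant population without ctDNA selection. Turning it into a reversion rate needs an assumed assay sensitivity and specificity. It also needs the false-positive result to be the baseline sample: if entry rests on an earlier sample, a baseline of zero leaves the ratio undefined. Estimates of halving by counting noise likewise rest on assumed molecule counts and flat ctDNA, and section 3.2.2 describes a personalized assay that averages several markers. None of this carries weight here.

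The consequence is limited too. Stage 2 also needs a sponsor judgement on risk and benefit, a pass leads only to possible expansion, and section 2.3 says μMeta cohorts may be included. Section 9.1 says the design aims to minimize false negatives, which argues against imposing a stricter cut-off.

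What survives is that the protocol states 0.001 for a μMeta test whose written rule gives 0.0052 at its own null, and offers no basis for that null.

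**Conclusion.** The point holds in a limited form. The 5% null is carried over to the 6-month ctDNA endpoint without support in the protocol, and 0.001 should not be quoted for μMeta. At the stated null the written rule has type I error 0.0052 and power 90%, for both cohort types. The stated 0.001 and 88% fit 7 or more of 35, which is a separate defect to reconcile for tdMeta as well.

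For μMeta the false-pass probability runs from 0.5% at a no-drug rate of 5%, through 2.4% at 7% and 9.8% at 10%, to 34% at 15%. It is at most 5% only up to a rate of about 8.4%. The binomial results are exact; the no-drug rates are assumed, and the protocol neither gives nor excludes any of them. Correcting the cut-off to 7 would not remove the dependence: the pass probability would still be 4.5% at 10% and 22% at 15%.

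**What to change.** In section 9.1:

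- Do not quote 0.001 for μMeta.
- State the null for the 6-month ctDNA endpoint separately from the ORR null, and give its basis.
- Report the μMeta pass probability of the chosen cut-off at no-drug rates of 5%, 10% and 15%.
- Reconcile cut-off and error rates for tdMeta as well: either keep 6 or more of 35 and state 0.005 and 90%, or change to 7 or more and keep 0.001 and 88%.

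Section 9.3.6 should be worded to match.

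A higher μMeta cut-off is an option for the sponsor to weigh, not a required change. For example, 8 or more of 35 gives a pass probability of 0.0175 at a 10% no-drug rate, with power 82% at 0.30. That is below the stated 88%, and a 10% null would need its own basis just as 5% does.

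The cost is wording, with the same 12 + 23 patients and no new procedures. The downside is a less favourable stated type I error if the cut-off of 6 is kept, or some loss of power if it is raised.

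### The two-stage rule in Section 9.1 (reject at 6 or more of 35) does not have the stated type I error of 0.001 or power of 88%; both figures belong to a rule of 7 or more

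*Protocol*

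**What the plan says.** Protocol Section 9.1 gives every element of the design in one paragraph:

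- Hypothesis: "The null hypothesis that the true response rate is 0.05 will be tested against a one-sided alternative".
- Stage 1: "In the first stage, 12 patients will be accrued per cohort", and "If there are 1 or fewer responses in these 12 patients, the study will be stopped for that cohort".
- Stage 2: "Otherwise, 23 additional patients will be accrued for a total of 35".
- Final decision: "The null hypothesis will be rejected if 6 or more responses are observed in 35 patients".
- Claimed properties: "This design yields a type I error rate of 0.001 and a power of 88% when the true response rate is 0.30".
- Method: "The binomial probability of observing an exact number of responses was used similar to that in a Simon's two-stage design".

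Section 9.3.6 repeats the 12-then-35 structure and the stage 1 stop ("If there is one response or no responses in these 12 participants as defined by CR or PR") but gives no final threshold. The 6-or-more sentence in Section 9.1 is therefore the only final success criterion in the protocol. It applies to both the tdMeta cohorts (objective response) and the μMeta cohorts (ctDNA response). The Synopsis plans 20 cohorts of 35, 700 participants in all.

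**The concern.** A fully specified two-stage binomial rule has exactly one type I error and one power at a given alternative. The paragraph gives both the rule and the two numbers, so they can be checked without outside information. They do not agree.

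This is the line that decides whether a cohort is a success, and the Synopsis and Section 2.2 say that efficacy signals may lead to expansion into adaptive or randomized studies. If the threshold and the error rates describe different rules, a cohort that ends with exactly 6 responses has two defensible readings. The protocol also claims tighter control of false positives than the written rule gives.

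**Working it through.** **Inputs (all from Section 9.1).** p0 = 0.05, one-sided; p1 = 0.30; n1 = 12; stop if X1 ≤ 1; n2 = 23; N = 35; reject if X1 + X2 ≥ c, with c = 6 as written.

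**Formula.** With X1 ~ Bin(12, p) and X2 ~ Bin(23, p) independent,

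P(reject | p) = Σ over x = 2 to 12 of P(X1 = x) × P(X2 ≥ c − x).

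At p = 0.05 this is the type I error and at p = 0.30 the power.

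**Type I error of the written rule (c = 6, p = 0.05).**

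| x | P(X1 = x) | P(X2 ≥ 6 − x) | product |
|---|---|---|---|
| 2 | 0.098792 | 0.025815 | 0.002550 |
| 3 | 0.017332 | 0.105174 | 0.001823 |
| 4 | 0.002052 | 0.320580 | 0.000658 |
| 5 | 0.000173 | 0.692643 | 0.000120 |
| 6 and above | 0.000011 | 1 | 0.000011 |
| Sum | | | **0.00516** |

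The first row alone, 0.00255, already exceeds the stated 0.001.

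**Same sum with c = 7, p = 0.05.** The products for x = 2 to 6 are 0.000487, 0.000447, 0.000216, 0.000055 and 0.000007. Later terms are negligible. The sum is **0.00121**.

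**Both properties for neighbouring thresholds.**

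| Reject at | Type I error (p = 0.05) | P(reject) at p = 0.10 | Power (p = 0.30) |
|---|---|---|---|
| ≥ 6 of 35 (as written) | 0.00516 | 0.098 | 0.9014 |
| ≥ 7 of 35 | 0.00121 | 0.045 | 0.8752 |
| ≥ 8 of 35 | 0.00023 | 0.017 | 0.8222 |
| **Stated** | **0.001** | not given | **0.88** |

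Only the 7-or-more rule reproduces both stated figures at their printed precision. Rounding cannot rescue the written rule: 0.00516 does not round to 0.001, nor 90.1% to 88%.

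**Other readings tried, keeping 6 or more.**

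- Ignoring the futility stop (single stage, 35 patients): type I error 0.0073, power 97.3%.
- Stopping at 0 of 12: 0.0068 and 96.3%.
- Stopping at 2 or fewer of 12: 0.0026 and 74.3%.
- First stage of 11 or 13 patients: 0.0047 and 87.5%, or 0.0055 and 92.1%.
- Total of 34 or 36 patients: 0.0046 and 89.8%, or 0.0058 and 90.4%.

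None gives 0.001.

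**The further condition in Section 9.3.6.** A minimum 10% response is also required before expansion. It does not change the calculation, because the 2 responses needed to pass stage 1 are already 2/12 = 16.7%. The sponsor's risk-benefit judgement named there has no numerical form and cannot enter a binomial calculation.

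**Size.**

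- Against the printed figure: 0.00516 / 0.001 = 5.2. Between the two rules: 0.00516 / 0.00121 = 4.3.
- The rules part only at exactly 6 of 35 after passing stage 1. That has probability 0.00516 − 0.00121 = 0.0039 at p = 0.05, 0.098 − 0.045 = 0.053 at p = 0.10, and 0.9014 − 0.8752 = 0.026 at p = 0.30.
- Over 20 independent cohorts, all null: 1 − (1 − 0.00516)^20 = 9.8% under the written rule; 1 − (1 − 0.001)^20 = 2.0% at the stated figure; 1 − (1 − 0.00121)^20 = 2.4% with 7 or more.

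**The case against.** The strongest reply accepts the arithmetic and disputes its weight.

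- **Direction of the error.** The document shows that the threshold and the figures disagree, not which was intended. In Simon's notation a boundary of 6 means rejection when responses exceed 6, and reading that as 6 or more would produce exactly this discrepancy. That is a likely origin, but an inference. Section 9.1 also says the design aims to keep false negatives low. The 6-or-more rule misses a 30% response rate 9.9% of the time, against 12.5% for 7 or more, so the stated aim suits the written threshold at least as well. This point stands, and it is why both corrections are offered.
- **Practical harm.** A one-sided per-cohort error of 0.005 is still small, the power is better than claimed, and the study seeks signals and is not meant to support a new indication (Section 8.2.10). That is true, but it does not make the stated error rate correct, and it does not settle how a 6-of-35 result is to be called.
- **Multiplicity.** The protocol evaluates cohorts independently and claims no family-wise control, and cohorts may be added, changed or discontinued. The 9.8% therefore illustrates the case of 20 null cohorts and breaches no stated guarantee. Comparing the two rules like for like, the contrast is 9.8% against 2.4%.
- **Left to the SAP.** The protocol itself states both the rule and its properties, and they conflict. An analysis plan that copied either would carry the conflict forward.

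**Conclusion.** The concern holds. As written, the rule has a type I error of 0.0052 and power of 90.1%, not 0.001 and 88%. With the protocol's own stage sizes and stage 1 bound, the stated pair belongs to a threshold of 7 or more.

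The per-cohort result needs no assumption beyond the inputs printed in Section 9.1 and independent binomial responses. The 20-cohort figures assume in addition that all planned cohorts open, all are null and all are independent. Which of the two elements was intended cannot be determined from the protocol.

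The error rate involved is small in absolute terms. But the only success criterion in the protocol and its quoted operating characteristics are incompatible, and the conclusion for a cohort with exactly 6 responses depends on which is kept. It must be corrected.

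**What to change.** The sponsor should establish which element was intended and amend Section 9.1 in one of two ways:

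1. Set rejection at 7 or more responses in 35. The stated type I error of 0.001 and power of 88% are then correct.
2. Keep 6 or more, and restate the type I error as about 0.005 and the power as about 90%.

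Either is a one-sentence change with no extra patients. The first raises the bar by one response and costs 2.6 points of power at a true rate of 0.30 compared with the rule as now written. The second accepts a less favourable stated type I error. The analysis plan should carry the same threshold.

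The choice should be made and documented before any cohort reads out. In an open-label study, settling it after a cohort has ended with 6 responses would be a data-driven choice of threshold.
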